## Version History

Version 2.0, 25Nov2021		
Chapter	Change Summary	Change Reason
2	Deleted secondary objective and exploratory objective.	The study is to monitor and assess the safety profile of Compound Sodium Picosulfate Granules in the real-world clinical practice. Secondary objective and explanatory objective are un-mandatory objective.
3	ePRO is replaced by contacting the subject remotely by pharmacist or hospital staff.  Deleted DeltaMed relevant description.	ePRO is too complicate for data entry by subjects, the protocol amendment is to simplify data collection method.  The DIM trial will be managed by Ferring.
4	Added hospitals as study sites.  Deleted planned 3000 subjects	Due to insufficient recruitment from pharmacies, to add hospitals for more subject recruitment.  Sponsor will collect as many subjects' safety data as possible.
5	Deleted variables "Patterns and compliance of drug use and liquid intake", "Date and time of X-ray examination, endoscopy or bowel surgery procedure" "Patient self-evaluation", etc.  Clarified the necessary study procedures.	Consistent with the updated trial objective.
6	Deleted "definition of Adverse Events of Special Interest".	The study will collect all Adverse Events reported from signing the ICF to about 37(+2) hours after the first medication.
7	Analysis Population "Registry population" and "Complete population" are replaced by "Safety population".  Deleted "Compliance of Drug Administration and Liquid Intake" and "Patient Self-evaluation"	Consistent with the updated trial objective
11	Deleted "The results will be submitted for publication in a peer-reviewed journal."	The study will not be used for publication
12	Added "Subject number will consist of study site code "CHN##" and study subjects code "####" (E.g. Subject number: CHN01-0001)"	Clarify subject number rule

## Non-Interventional Study (NIS) Protocol

Others	Deleted ePRO relevant description. Deleted DeltaMed relevant description. Added hospitals as study sites.	Consistent with the updated protocol.
Version 1.0, 19Nov2020		

## SYNOPSIS

**TITLE OF STUDY**

A post-marketing drug intensive monitoring study of Compound Sodium Picosulfate Granules for bowel preparation in Chinese population

**SIGNATORY INVESTIGATOR(S)**

Not applicable

**STUDY SITE(S)**

The study is planned to be carried out in 20 pharmacies and hospitals in Chinese mainland.

**PLANNED STUDY PERIOD**

Apr 2021- Dec2022

**OBJECTIVES**

To monitor and assess the safety profile of Compound Sodium Picosulfate Granules in the real-world clinical practice in Chinese population.

**METHODOLOGY**

This is a post-marketing multi-site, prospective, non-interventional study. Compound Sodium Picosulfate granules or other similar drugs will be prescribed to the subject based on physicians' clinical judgement.

The study will collect all stipulated events reported from signing the informed consent form (ICF) to about 37(+2) hours after first medication. Contacting the subject remotely by pharmacist or hospital staff will be used to collect adverse events/reactions and other relevant information. No additional tests or examinations will be performed on subjects, no drugs will be provided to the subjects.

- The study staff will register the eligible subjects. The subjects will sign the informed consent, provide contact information. Demographic characteristics (gender, age, nation, height, weight) of subjects will be collected.
- Contact the subjects remotely 37(+2) hours after first medication to collect any adverse events and information on the Compound Sodium Picosulfate granules administration.

All adverse events collected will be sent to the sponsor for case processing.

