#### 3.2 Medicinal Product

This study does not provide treatment, the subjects must already have been prescribed Ferring Compound Sodium Picosulfate Granules. All directions for drug usage are solely at the discretion of the subject's primary physician in accordance with his/her usual practice and should be consistent with the local prescribing information.

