#### 3.3 Bias and Limitations

##### 3.3.1 *Method to Minimize Bias*

In order to limit this potential selection bias in the recruitment of subjects, the recruiter will be required to include all subjects who have been prescribed Ferring Compound Sodium Picosulfate Granules in a naturalistic fashion.

Since the AE information is collected through the report of subjects, while the missing information of AEs due to subjects failing to declare may be immeasurable.

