## 4 SELECTION OF STUDY POPULATION

### 4.1 Study Population

#### 4.1.1 *Inclusion Criteria*

- 1) Agree to participate in this study and sign the ICF by subject or the legal representative.
- 2) Subjects taking the compound sodium picosulfate granules drug in real clinical practice.

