#### 4.1.2 *Exclusion Criteria*

- 1) Subjects who are enrolled in other on-going studies, which prohibit any participation in this non-interventional study.

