### ***6.7.4 Assessment of AE***

#### **Causality Classification**

Subject will assess causal relationship between the medicinal product and each AE, and answer “yes” or “no” to the question “Do you consider that there is a reasonable possibility that the event may have been caused by Compound Sodium Picosulfate Granules?”

During case processing, the sponsor will also assess the causality. The relationship of an AE with the medicinal product will be classified according to the following:

– **Related:** The AE follows a reasonable temporal sequence from the medicinal administration and cannot be reasonably explained by the subject's clinical state or other factors (e.g. disease under study, concurrent diseases, and concomitant medications). It may be a known reaction to the drug under study or its chemical group or is predicted by known pharmacology and could not be ruled out with certainty.

– **Not related:** The AE does not follow a reasonable sequence from the medicinal product administration or can be reasonably explained by the subject's clinical state or other factors (e.g. disease under study, concurrent diseases, and concomitant medications).

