### 7.2 Analysis Population Definitions

- **Safety population:** Subjects who has signed an ICF and has at least partially taken the drug. It is the primary population for safety evaluation in post-marketing intensive monitoring.

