**Summary of monitoring methods:**

This is a post-marketing multi-centre, prospective, non-interventional study. Subjects who have been prescribed Ferring Compound Sodium Picosulfate Granules at the participating sites will be enrolled. The study will collect all stipulated events reported from signing the ICF to about 37(+2) hours after first medication. Pharmacist or hospital staff will contact subjects remotely to collect adverse events/reactions and other relevant information. No additional tests or examinations will be performed on subjects.

- The investigational personnel (e.g. pharmacy pharmacist or hospital staff) will register the eligible subjects. The subjects will sign the informed consent, record contact information.
- After the procedure (about 37 (+2) hours after first drug administration) will report any adverse events and relevant information.
- Follow up, if necessary, pharmacist or hospital staff will collect AEs and other relevant information.

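### Use of a second bowel-cleansing agent is neither excluded nor recorded for every subject, so incidence on the product alone could not be calculated afterwards

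*Combined protocol and SAP*

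**What the plan says.** **Eligibility.** Inclusion criterion 2 in Section 4.1.1 reads "Subjects taking the compound sodium picosulfate granules drug in real clinical practice". The only exclusion criterion (Section 4.1.2) is "Subjects who are enrolled in other on-going studies, which prohibit any participation in this non-interventional study". Neither mentions use of another cleansing agent.

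**Product.** Section 3.2 says "the subjects must already have been prescribed Ferring Compound Sodium Picosulfate Granules". Section 3.3.1 tells the recruiter to "include all subjects who have been prescribed Ferring Compound Sodium Picosulfate Granules", and the appendix synopsis says "Subjects who have been prescribed Ferring Compound Sodium Picosulfate Granules at the participating sites will be enrolled". The main synopsis says that "Compound Sodium Picosulfate granules or other similar drugs will be prescribed to the subject".

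**Data collected.** Section 5 lists demographics for every registered subject. It places dose and timing, indication, concomitant medications and medical history under subjects who had an AE. The synopsis adds, for all subjects, information on how the granules were taken. Sections 3.1 and 8 speak of medications in general. Section 6.10 requires lack of efficacy, off-label use, underdose and non-compliance to be recorded even without an AE. None of these places names a second cleanser.

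**Analysis.** The Safety population is "Subjects who has signed an ICF and has at least partially taken the drug". Section 7.3 presents results overall. Section 7.3.3 adds unspecified specific populations and an open list of covariates that does not include another cleanser. (Section 7.3.3 also refers to a registry population that Section 7.2 does not define; that is a separate matter and does not separate co-users either.)

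**Causality.** Under Section 6.7.4 the sponsor may class an AE as not related if it "can be reasonably explained by the subject's clinical state or other factors (e.g. disease under study, concurrent diseases, and concomitant medications").

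**The concern.** The first objective in Section 2 is the incidence of known ADRs. Section 3.3.2 acknowledges that the study has one arm and no comparator, so the rates depend on how well exposure to the product is characterised. A subject who takes some of the granules and then another preparation meets both inclusion criteria and counts in full in the Safety population.

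The documents give no frequency for this, but they describe circumstances in which it could happen. Section 1.1 lists other agents in use (PEG electrolyte powder, magnesium salt, sodium phosphate, mannitol, herbal medicine). Section 6.10 expects some reports of inadequate effect. Section 3.2 leaves drug use to the physician's usual practice.

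At stake is whether a reader of the report can tell how often reactions occur in people who took only this product. If co-use is recorded only in subjects with an AE, that question cannot be answered at the analysis stage, however carefully each case is assessed.

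**Working it through.** The plan states no sample size, event rate or precision on this point, so there is no figure to reproduce. Step 1 is algebra on what is collected. Steps 2 to 4 are illustrations on assumed inputs.

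**Step 1: what can be computed from the data as listed in Section 5.** Let N be the Safety population, A the subjects with an AE, m1 the co-users with an AE and m0 the co-users without one.

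Product-alone incidence = (A − m1) / (N − m1 − m0).

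N, A and m1 are available. m0 is not, because Section 5 does not list concomitant medications for subjects without an AE. If some sites follow the broader wording of Sections 3.1 and 8, m0 would be partly known, and unevenly by site.

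**Step 2: how far the pooled rate could differ.** Let f be the share of co-users and RR the AE risk with co-use relative to the product alone.

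Pooled incidence = p_alone × [1 + f × (RR − 1)].

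Neither f nor RR is in the documents. Assumed ranges: f from 5% to 30%, RR from 1 to 3. The excess of pooled over product-alone incidence is:

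| f | RR = 1 | RR = 1.5 | RR = 2 | RR = 3 |
|---|---|---|---|---|
| 5% | 0% | 2.5% | 5% | 10% |
| 10% | 0% | 5% | 10% | 20% |
| 20% | 0% | 10% | 20% | 40% |
| 30% | 0% | 15% | 30% | 60% |

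Example: f = 20%, RR = 3 gives 1 + 0.20 × 2 = 1.40.

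**Step 3: would a frequency class change?** The table in Section 1.2.3 separates common from uncommon at 1/100. Take an assumed product-alone rate of 0.8%. Over RR 1.5 to 3 the pooled rate runs from 0.8% × 1.025 = 0.82% to 0.8% × 1.60 = 1.28%. It passes 1% in only three cells: f = 20% with RR = 3 (1.12%), f = 30% with RR = 2 (1.04%) and f = 30% with RR = 3 (1.28%).

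**Step 4: the opposite direction, for ADRs.** If every event in a co-user were classed as not related while the subject stayed in the denominator, the ADR rate would be p_alone × (1 − f). That is 5% too low at f = 5% and 30% too low at f = 30%. It is an extreme case: under Section 6.2 the reporter's suspicion alone can make an event an ADR.

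**The case against.** The strongest reply is that the study aims at safety in real-world practice (Section 2) under general population surveillance (Section 7.1), and co-medication belongs to real-world use. On that view the overall rate is the intended result, and no section sets the product alone as the reference. This stands: the overall Safety-population incidence should remain the main result. It does not meet the point that a product-alone figure, which a reader of a single-product safety report may well want, would be out of reach.

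Second, capture is not absent. Section 6.10 would pick up some failed or partial preparations without an AE, and Sections 3.1 and 8 mention medications without limiting them to AE cases. This also stands in part: capture is incomplete rather than nil. Since none of these places names another cleanser, it cannot be relied on for a denominator.

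Third, causality assessment already weighs concomitant medications. That helps with individual cases, but it leaves the subject in the ADR denominator and does not alter AE counts, which Section 7.3.3 reports whether or not related.

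Two stronger readings are tempting and are not supported:

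- A reader might infer from the synopsis phrase on similar drugs that users of other products are enrolled, or that products are combined. The word is *or*: it describes a choice in prescribing, and enrolment still requires taking the granules.
- A reader might infer from criterion 2 that another maker's granules could enter the data. Sections 3.2 and 3.3.1 and the appendix already restrict the study to the sponsor's product, so this is a mismatch of wording and not an open route.

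**Conclusion.** The point holds as a gap in data collection and presentation. Co-use of another cleanser is not excluded, not separated in the analysis and, as Section 5 is written, not recorded for subjects without an AE. Product-alone incidence therefore could not be reliably calculated afterwards.

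Its practical importance is unknown. Under the assumed ranges the pooled AE incidence is 0% to 60% above the product-alone value. It is exactly equal if co-use does not change the risk (RR = 1), whatever the share. An RR below 1, which the documents do not rule out, would reverse the sign.

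It would go too far to conclude that the planned overall incidence is wrong or biased by a stated amount: nothing in the documents shows that co-use is common or that it raises the risk. This is a cheap improvement and not an error in the planned analysis.

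**What to change.** 1. **Collect.** In Section 5, at the existing 37(+2)-hour contact, ask every subject whether any other bowel-cleansing agent, laxative or enema was taken for this procedure, which one, and whether before or after the sachets.
2. **Report.** In Section 7.3.3, keep the overall Safety-population incidence as the main result and add AE and ADR incidence for subjects who took the product alone. Show subjects with no answer, including any contacted before the change, as not known; do not count them as product-alone.
3. **Align the wording (secondary).** Name the sponsor's product in criterion 2 (synopsis and Section 4.1.1), state what is meant by the drug in Section 7.2, and delete or clarify the reference to similar drugs in the synopsis, so that all three agree with Sections 3.2 and 3.3.1 and the appendix.

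Cost: one more data item in a contact that already takes place, one extra column in the AE tables, and a slightly smaller number of subjects in that column. Enrolment, treatment and examinations do not change.

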**NUMBER OF SUBJECTS**

Sponsor will collect as many subjects' safety data as possible.

**CRITERIA FOR INCLUSION / EXCLUSION**

Inclusion criteria:

- Agree to participate in this study and sign the ICF by subject or the legal representative.
- Subjects taking the Compound Sodium Picosulfate Granules drug in real clinical practice.

Exclusion criteria:

- Subjects who are enrolled in other on-going studies, which prohibit any participation in this non-interventional study.

## **MONITORING PRODUCT**

Compound Sodium Picosulfate Granules

## **DURATION OF PARTICIPATION**

The duration of participation for each subject will be from signing the ICF to about 37(+2) hours after first medication. The sponsor will decide on the requirement for any follow-up of AEs persisting.

## **STATISTICAL METHODS**

As this is a descriptive study, no formal statistical testing will be carried out.

Descriptive statistics on continuous data will include the counts, number of missing data, means, standard deviations, medians, minimum and maximum values, while categorical data will be summarized using frequency counts and percentages.

Adverse events (AE) will be coded according to the latest version of the MedDRA dictionary and presented in "preferred term (PT) and system organ class (SOC)". The incidence of each AE will be calculated.

## LIST OF ABBREVIATIONS

ADR	Adverse drug reaction
AE	Adverse event
AESI	Adverse event of special interest
BHPM	Bis-(p-hydroxyphenyl)-pyridyl-2-methane
BMI	Body Mass Index
CRO	Contract research organization
EC	Ethics committee
ECG	Electrocardiogram
ePRO	Electronic patient reported outcomes
FDA	U.S. Food and drug administration
GPP	Good pharmacoepidemiology practice
ICF	Informed consent form
ICSR	Individual case safety report
INR	International standardized ratio
NMPA	National medical products administration
PEG	Polyethylene glycol
PSUR	Periodic safety update report
PT	Preferred terms
RA	Regulatory authority
RMP	Risk management plan
SAE	Serious adverse event
SADR	Serious adverse drug reaction
SMP	Safety management plan
SOC	System organ classification
SOP	Standard operating procedure

## 1 INTRODUCTION

### 1.1 Background

High-quality bowel preparation plays an important role in ensuring a safe and successful X-ray examination, endoscopy or some kinds of bowel surgeries. Inadequate bowel preparation may lead to incomplete examination of the colonic mucosa, may require increased operation time and difficulty, and incur the costs for rescheduling or performing other examinations. Early attention to the influencing factors of bowel cleansing effect and taking positive measures can effectively improve the success rate and diagnosis rate of endoscopic and radiological examinations, and reduce the possibility of postoperative complications and local infections. In 2019, China released the latest "Guidelines for Bowel Preparation Related to Digestive Endoscopy", emphasizing the importance of dietary restrictions and patient notification and education. The "Guideline" also recommends that sodium picosulfate, magnesium oxide, and anhydrous citric acid can be used for bowel preparation before endoscopy and is well tolerated (recommended strength: weak; evidence quality: moderate). The other used colonic cleansing agents also include polyethylene glycol (PEG) electrolyte powder, magnesium salt, sodium phosphate, mannitol and Chinese herbal medicine. Each carries its own properties, indications and safety profiles.

Compound Sodium Picosulfate Granules is a compounded preparation consisting of sodium picosulfate and magnesium citrate. Each sachet contains 10 mg of sodium picosulfate, 3.5 g of magnesium oxide and 12.0 g of citric acid. It is white to slightly yellow crystalline powder, with a slight orange flavour. Sodium picosulfate is transformed by colonic bacteria to form an active metabolite: bis-(p-hydroxyphenyl)-pyridyl-2-methane, BHPM, which acts directly on the colonic mucosa to stimulate colonic peristalsis. Magnesium oxide and citric acid react to create magnesium citrate (when dispersed in a solution), which is an osmotic agent that causes water to be retained within the gastrointestinal tract. The stimulant laxative activity of sodium picosulfate together with the osmotic laxative activity of magnesium citrate produces a purgative effect, which can be used to clean the bowel prior to X-ray examination, endoscopy or bowel surgery.

Since its first marketing in the UK in December 1980, Compound Sodium Picosulfate Granules has been approved in more than 80 countries and regions, including Germany (2010), France (2010), Spain (2011), Italy (2011) and the United States (2012), Japan (2016), under the tradename PICOLAX, PICOPREP or PREPOPIK. In 2018, Compound Sodium Picosulfate Granules was officially approved in China with the indication: for preparation of bowel cleansing prior to X-ray examination, endoscopy or surgery when judged clinically necessary.

## 1.2 Preliminary Safety Evaluation

### 1.2.1 *Preclinical Safety Data*

The preclinical safety data related to Compound Sodium Picosulfate Granules are summarized as follows:

#### **General Safety Pharmacology**

Anesthetized rats were injected with sodium picosulfate intravenously and tested their cardiac function parameters. Under the maximum dose of 160 mg/kg, no abnormal changes in blood pressure and electrocardiogram were observed .

Irwin screen test was used to evaluate the effect of one-time oral gavage of sodium picosulfate on the central nervous system of mice. Single oral administration of sodium picosulfate 40mg/kg and 80mg/kg in mice has no effect on the central nervous system .

In a 4-week repeated oral dose toxicity study of Compound Sodium Picosulfate Granules in dogs (n = 6), no abnormal ECG changes were observed under the maximum dose of 1000 mg/kg (twice a day, every 8 hours apart).

#### **Repeat-Dose Toxicity**

Repeated dose toxicity studies with sodium picosulfate (2 weeks) and Compound Sodium Picosulfate Granules (4 weeks) in both the rat and the dog showed expected treatment and dose related pharmacology with soft stools and diarrhoea and with no observed adverse effects.

#### **Carcinogenicity**

No published studies of carcinogenic potential of sodium picosulfate have been identified.

#### **Genotoxicity**

Sodium picosulfate was not mutagenic in the Ames test, the mouse lymphoma assay and the mouse bone marrow micronucleus test.

#### **Reproductive toxicity**

Male and female rat fertility was not affected by oral doses of sodium picosulfate up to 100 mg/kg.

Prenatal developmental studies in rats and rabbits did not reveal any teratogenic potential after oral dosing of sodium picosulfate, but embryotoxicity has been observed in rats at 1000 and 10000 mg/kg/day and in rabbits at 1000 mg/kg/day. The corresponding safety margins were 3000 to 30000 times the anticipated human dose. In rats, daily doses of 10 mg/kg during late gestation (fetal development) and lactation reduced body weights and survival of the offspring.

In an oral fertility study in rats, Compound Sodium Picosulfate Granules did not cause any significant adverse effect on male or female fertility parameters up to a maximum dose of 2000 mg/kg twice daily (about 1.2 times the recommended human dose based on the body surface area). During the perinatal period, rats were given Compound Sodium Picosulfate Granules 2000 mg/kg twice daily, and no significant effect on pup growth and development was observed.

